Recently, after having demonstrated a sedative effect (1), a multi-center, randomized, double-blind, sham-controlled trial has shown the efficacy and safety of external trigeminal nerve stimulation (e-TNS) with the Cefaly® device for the preventive treatment of episodic migraine (2). Safety and patient satisfaction has been further confirmed by a prospective study on 2,313 patients (3).

Many patients in Europe have reported benefit using the device only during attacks. In past few years, small studies have been performed using the Cefaly® device as an acute treatment:

- A medical lab in France ("Spincontrol") implemented an open clinical trial during 28 days on 32 patients suffering from frequent tension-type headache but not migraine. 66% reported pain relief using the device during an attack.
- University of Liege conducted a pilot trial on migraine patients (4). Ten patients were asked to apply the Cefaly® device as an acute treatment for 3 attacks. Electro-stimulation provided complete pain relief in 13% of attacks, delayed the need for acute medication use by more than 30 minutes in 20%, had no effect in 57% and increased the pain in 10%. However, there were flaws in the protocol design, including the short duration of the session (20 minutes), which is not sufficient to provide relief based on experiential feedback from migraineurs. In addition, the number of attacks treated was too small, as patients may require several sessions to adapt to and allow the intensity of stimulation to rise to a therapeutic level (otherwise it is under a minimum threshold of efficacy).
- Kozminsky (5) assessed whether the Cefaly® device was effective and well-tolerated as rescue therapy for migraine symptoms lasting 72 hours or longer. t-SNS (or e-TNS) therapy with the Cefaly device brought about a reduction of migraine-related pain (average minus 46%) as rescue therapy in these patients. e-TNS therapy via the Cefaly® device was well-tolerated, and most patients reported that they would consider home therapy if it were affordable.
- Since March 2015, an open-label pilot trial on the acute treatment of migraine using the Cefaly® device has been underway at Columbia University, NY. Patients experiencing a migraine attack for at least 3 hours (without use of acute medications during this time) and having stable pain intensity for at least 1 hour, are eligible to receive a 60-minute stimulation to treat their attack. Pain is assessed on a 10-point visual analogue scale (VAS) before, after the 1-hour treatment, and 2 hours after the beginning of the treatment. The study is still on-going, but the results to date confirm prior observations that e-TNS therapy via the Cefaly® device can significantly reduce pain intensity during an acute migraine attack, as measured via the VAS.

Based on the data from the above studies and preliminary findings from the open-label pilot trial at Columbia, it is reasonable to further investigate the efficacy of e-TNS with the Cefaly® device as an acute treatment for migraine via a double-blind, randomized, sham-controlled trial.

2. Study objective

The main objective of this study is to assess the efficacy of the Cefaly® device as an acute treatment of migraine attack in adult patients.

3. Study outcomes

Primary outcome:

- Mean change of pain score at 1 hour compared to baseline

Secondary outcomes:

- Proportion of patients not having required rescue medication at 2 hours
- Mean change of pain score at 2 hours compared to baseline (if rescue therapy was not used)
- Proportion of patients not having required rescue medication within 24 hours
- Mean change of pain score at 24 hours compared to baseline (if rescue therapy was not used)

4. Study design

4.1. General description

This study is a clinical study with the following characteristics:

- Multi-center (4 investigation sites)
- Prospective
- Double-blind
- Sham-controlled
- Randomized

4.2. Experimental protocol

Patients having a stabilized migraine attack will be recruited during a standard care visit or at an on-demand appointment. They will report their pain score before the treatment (recruitment phase), after 1 hour of treatment (acute treatment phase) and finally 2 hours after the beginning of the treatment (post-treatment phase). At that moment (2 hours after the beginning of the treatment), patients will receive rescue medication if necessary. Rescue medication intake will be reported during the 24 hours following the beginning of the treatment. Pain score at 24 hours after the treatment will be reported as well. The overall study flow is illustrated in Figure 1. During the different phases the investigator will monitor adverse events.

4.2.1. Recruitment phase

Two options are available to recruit patients:

- Eligible patients can be recruited during a standard care visit if they are experiencing a migraine attack having lasted at least 3 hours, with pain stabilized for at least 1 hour, and have not used acute migraine medication within the past 3 hours.
- Patients can also be screened beforehand (having been informed about the study at a standard visit or via advertisement), and arrange for an on-demand appointment when they are undergoing an attack for at least 3 hours, with pain stabilized for at least 1 hour.

Patient will receive the information and consent documents and have to sign these documents before study procedures are initiated. Then the investigator will verify that the patient meets all inclusion criteria and none of the exclusion criteria. If this is the case, the patient has to give a value on an 11-point visual analog scale (VAS) (0 = no pain, 10 = maximum pain) of the current pain associated with the migraine attack.

The patient will then be randomized to either the verum or the sham group. To this end, a unique device will be allocated to him/her.

The investigator will then apply the device on the patient and start the stimulation. If the patient cannot bear the paresthesia of the neurostimulation (needs to stabilize intensity before 4 minutes i.e. nociceptive threshold < 5 mA for impulse width of 250 μ s), the patient is considered meeting the exclusion criteria of allodynia (too low nociceptive threshold). The patient is in this case not included in the trial.

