4.2.2. Acute treatment phase

When the patient bears more than 4 minutes of neurostimulation, he/she is included in the trial, and the neurostimulation continues for the 56 remaining minutes of the stimulation. The patient will be randomized to receive either:

- Verum stimulation, with square pulse current (100 Hz, 250 μ s) at a linearly increasing intensity starting at 0 mA up to a maximum of 16 mA after 14 minutes, then remaining stable for the rest of the session (46 minutes), OR
- Sham stimulation with felt paresthesia.

At the end of the one-hour treatment period the patient gives again an estimate of the pain on the same VAS.

During the treatment, the patient can stabilize the intensity by pressing the button or can stop the treatment. The device can also be stopped accidentally, what interrupts the treatment. When stopped, voluntarily or accidentally, the device may not be restarted.

Duration, intensity and/or interruption will be recorded for each patient thanks to a built-in electronic system in the device.

In any case, the patient gives the estimate of the pain after 60 minutes.

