5.2. Exclusion criteria

The following exclusion criteria apply:

1. Pregnant women
2. Patients having received Botox treatment in the prior 4 months
3. Patients having received supraorbital nerve blocks in the prior 4 months
4. Diagnosis of other primary or secondary headache disorders, except of Medication Overuse Headache
5. Patients with only temporal or occipital headache
6. Patients using opioid medication
7. Patients having taken abortive migraine medication in the prior 3 hours
8. Allodynia: intolerance to supraorbital neurostimulation (allodynia) that makes the treatment not applicable (the patients will be excluded if they are unable to tolerate the first 5 minutes of neurostimulation).
9. Implanted metal or electrical devices in the head
10. Cardiac pacemaker or implanted or wearable defibrillator
11. Patient having had a previous experience with Cefaly®

6. Medical device and treatment

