6.4. Use during the trial

The investigator will apply the device on the patient's head. A session of 60 minutes will be applied. If the patient experiences discomfort during the stimulation, he or she can stabilize the intensity of stimulation at any time by pushing the "on" button of the device (the current intensity will then remain stable until the end of the session). The patient should at least let the device increases the intensity for 4 minutes in order to be included in the trial: before this point, the patient's nociceptive threshold is considered too low because of allodynia.

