8.2.2. Statistical methods

- All relevant general, safety and efficacy data will be descriptively summarized at each time point.
- Continuous data will be summarized by the number of subjects (N), the arithmetic mean, the standard deviation, the coefficient of variation as a percentage (CV%), the median, the inter-quartile range, the minimum and the maximum value.
- Categorical data will be summarized by absolute (N) and relative (%) frequency tables.
- Where considered as relevant, the study data will also be graphically depicted.

- Imputation of missing data will be performed according to the last value carried forward method.
- Analyses will be conducted on an intent-to-treat (ITT) basis, i.e. including all subjects who used the study device for more than 4 minutes (see in exclusion criteria 8. Allodynia), did not take rescue medication before the 1 hour and reported pain at 1 hour.
- A sub-analysis of the per-protocol patients (those receiving the complete 1-hour treatment) will be performed as well.

9. Management of adverse events

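### The set called ITT is selected after randomisation, and the tolerance cut-off that helps define it is 4 minutes in four sections but 5 minutes in exclusion criterion 8

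*Combined protocol and SAP*

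**What the plan says.** Section 4.2.1 checks eligibility, takes the baseline pain score and then states: "The patient will then be randomized to either the verum or the sham group". The mechanism is allocation of a unique device. Stimulation starts on that device, and a patient who has to stabilise the intensity before 4 minutes is treated as meeting the allodynia exclusion: "The patient is in this case not included in the trial".

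Section 4.2.2 admits the patient once 4 minutes are passed, and "the neurostimulation continues for the 56 remaining minutes of the stimulation". It then mentions randomisation a second time.

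Section 8.2.2 defines the ITT set as patients who "used the study device for more than 4 minutes (see in exclusion criteria 8. Allodynia"), took no rescue before 1 hour and reported pain at 1 hour. Section 4.2.4 also makes early rescue, leaving without a 1-hour score, and an accidental device stop into drop-outs.

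On the cut-off, section 6.4 says: "The patient should at least let the device increases the intensity for 4 minutes in order to be included in the trial". Exclusion criterion 8 in section 5.2 says: "the patients will be excluded if they are unable to tolerate the first 5 minutes of neurostimulation".

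**The concern.** Intention-to-treat means analysing everyone randomised, in the arm allocated. Here every condition for entering the set is observed after allocation, and the tolerance step is judged on the allocated stimulation itself. Section 7.3 says the arms differ in pulse frequency, so failures could differ by arm. If they do, and if early intolerance is related to how pain evolves, the 1-hour comparison is no longer protected by randomisation. Early rescue is more plainly related to the outcome than intolerance is.

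The text does not commit to reporting removals by arm, so a reader could not tell whether this happened. Separately, sites working from criterion 8 and sites working from 4.2.1 could remove different patients.

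**Working it through.** **Order of events.** In 4.2.1 the sequence is eligibility, baseline score, allocation of a device, stimulation, tolerance step, removal. In 4.2.2 randomisation is mentioned after the 4 minutes. That conflicts with 4.2.1, but 4.2.2 continues the same session and describes neither a common run-in device nor a second allocation. Section 6.7 supplies devices as verum or sham and does not let one be reused on another patient. The only device described for the first 4 minutes is therefore the allocated one.

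**Cut-off.** Section 4.2.2 gives the verum ramp as 0 to 16 mA over 14 minutes, or 16/14 = 1.143 mA per minute.
- 4 minutes: 4 × 1.143 = 4.57 mA.
- 5 minutes: 5 × 1.143 = 5.71 mA.
- The 5 mA gloss in 4.2.1: 5 × 14/16 = 4.375 minutes.

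The three descriptions do not coincide. A patient who gets past 4 minutes but cannot tolerate the fifth is in under four sections and out under criterion 8, the criterion 8.2.2 cites for its 4 minutes. The definition varies too: 4.2.1 turns on stabilising the intensity, 8.2.2 on duration of use. A patient who stabilises at 3 minutes and completes the hour fails the first and meets the second.

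**The plan's sample size.** Section 8.2.1 gives rescue rates of 71% and 41.33%, two-sided 5%, power 80%. With mean proportion 0.5617, n = [1.96√(2 × 0.5617 × 0.4383) + 0.842√(0.71 × 0.29 + 0.4133 × 0.5867)]² / 0.2967² = 42.7, so 43 per arm as stated. Power at 45 per arm is 82.1%. The 17 per arm for pain also reproduces, from the 2-hour difference of 2.40 with SD 2.42 (16.98 by t-test).

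**Illustrative bias.** The removal shares q and the correlation ρ between intolerance and 1-hour change are assumptions; the documents give neither. Take normal intolerance with the top share q removed, no true effect, SD 2.42 and 45 analysed per arm. The mean displacement in units of intolerance is λ(q) = φ(z)/(1 − q), where z is the upper q point: λ(0.02) = 0.049, λ(0.05) = 0.109, λ(0.10) = 0.195, λ(0.20) = 0.350. The shift is ρ × 2.42 × the difference in λ. With SE = 2.42√(2/45) = 0.510, type I error ≈ Φ(−1.96 + shift/SE) + Φ(−1.96 − shift/SE).

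| Removed, by arm | ρ | Shift (points) | Formula | Simulation |
|---|---|---|---|---|
| 10% v 2% | 0.3 | 0.106 | 5.5% | 5.4–5.5% |
| 10% v 2% | 0.5 | 0.176 | 6.4% | 6.4% |
| 20% v 5% | 0.3 | 0.175 | 6.4% | 6.3–6.5% |
| 20% v 5% | 0.5 | 0.292 | 8.8% | 9.0–9.2% |
| 10% v 10% | 0.3, 0.5 | 0 | 5.0% | 4.9–5.1% |

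**Who the 90 counts.** Section 5 says 90 are included, 4.2.2 uses that word only after 4 minutes, and 8.2.1 says 90 are recruited. At 10% v 2% removed (assumed):
- If 90 are allocated, 45 × 0.90 = 40.5 and 45 × 0.98 = 44.1 pass. The pooled proportion is 0.568, the null SE 0.1078 and the alternative SE 0.1032, so power for rescue is Φ((0.2967 − 1.96 × 0.1078)/0.1032) = 79.6%.
- If 90 must pass, 90/(0.90 + 0.98) = 47.9 per arm, about 96 in all, must be allocated.

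**Does analysing everyone cure it?** Only with a rule for incomplete data, as simulation under no effect shows for 10% v 2% and 20% v 5% removed.
- Observed scores for all, untouched by rescue: type I error about 5%, shift 0.00.
- If 80% of removed patients take rescue and gain 2 extra points (assumed, ρ = 0.3), raw scores give shifts of 0.13 and 0.24 and type I error of about 5.8% and 7.5%. The current set gives 0.11 and about 5.5%, and 0.17 and about 6.4%.
- Setting every removed patient to no change, with both arms improving 2 points and ρ = 0, shifts the result by 0.16 and 0.30 points against the arm with more removals; type I error is about 6% and 9% to 10%. The section 8.2.2 rule, "Imputation of missing data will be performed according to the last value carried forward method", amounts to this for a removed patient with only a baseline score.

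**The case against.** The step is pre-specified, precedes any post-baseline score, and is judged by blinded patients and staff. Sections 6.5 and 7.3 describe similar sham paresthesia and a 128-subject trial in which patients could not tell the devices apart. That makes unequal removal less likely, and it stands. It does not settle the matter, because what is reported is inability to distinguish the devices, not early tolerance.

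Section 8.2.2 spells out its conditions beside the label, so nothing is concealed. That also stands: the name is wrong, but the definition is open.

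Section 4.2.2 can be read as randomising after the tolerance step. With no common run-in described, that reading does not restore an intention-to-treat set; it adds a conflict to resolve.

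The flowchart is not shown and the CRF is an annex, so either might clarify the order or the recording of removals. Device numbers (8.1) and device logs (4.2.2: "Duration, intensity and/or interruption will be recorded for each patient") would already allow a count by arm.

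A reader might go further and infer that the selection favours verum, or that all allocated patients must become the primary set. The documents support neither. They give no failure rates, and the remedy can be as biased as the current set if removed patients take early rescue.

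**Conclusion.** The label and the cut-off are wrong as written. That rests on the text alone and needs no assumption. Tolerance failure, rescue before 1 hour and a missing 1-hour score all act after allocation. Accidental stops are a further loss under 4.2.4, although 8.2.2 does not list them and 4.2.2 still asks for the 60-minute score, so their status needs stating.

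The bias is a possibility of unknown size and direction. Over the assumed range, type I error is about 5.5% to 9% and the shift 0.1 to 0.3 points. That does not approach the planned 2.83, so it would be wrong to infer that selection at the tolerance step could produce an effect of that size. Those figures cover tolerance failure only; loss through early rescue was not modelled.

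The ambiguity over the 90 matters mainly for rescue use, which sets the sample size with a margin of only 2 per arm over 43. At the assumed 10% v 2%, power is 79.6%, just under the stated 80%.

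**What to change.** 1. Rename the section 8.2.2 set, for example modified ITT, and do not call it ITT.
2. Report by arm, from device numbers and logs, how many were allocated and how many were removed for each reason: tolerance failure, rescue before 1 hour, no 1-hour score, accidental stop.
3. Add a pre-specified sensitivity analysis of all allocated patients by allocated device. Ask removed patients for a 1-hour score and rescue use, as data collection only. State a rule for missing scores and for scores given after rescue, and vary it over a range. Neither no change nor raw post-rescue scores should stand alone.
4. State whether 90 counts allocated or tolerance-passed patients.
5. Reconcile 4.2.1, 4.2.2, exclusion criterion 8, 6.4 and 8.2.2 to one threshold, one definition and one order of events. The sponsor must state which is intended.

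The cost is wording changes, a few more patients to contact and one extra analysis. If the 90 is to count patients who pass, a few more devices are needed: about 96 allocations at the assumed 10% v 2%.

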4.2.2. Acute treatment phase

When the patient bears more than 4 minutes of neurostimulation, he/she is included in the trial, and the neurostimulation continues for the 56 remaining minutes of the stimulation. The patient will be randomized to receive either:

- Verum stimulation, with square pulse current (100 Hz, 250 μ s) at a linearly increasing intensity starting at 0 mA up to a maximum of 16 mA after 14 minutes, then remaining stable for the rest of the session (46 minutes), OR
- Sham stimulation with felt paresthesia.

At the end of the one-hour treatment period the patient gives again an estimate of the pain on the same VAS.

During the treatment, the patient can stabilize the intensity by pressing the button or can stop the treatment. The device can also be stopped accidentally, what interrupts the treatment. When stopped, voluntarily or accidentally, the device may not be restarted.

Duration, intensity and/or interruption will be recorded for each patient thanks to a built-in electronic system in the device.

In any case, the patient gives the estimate of the pain after 60 minutes.

4.2.3. Post-treatment phase

Two hours after the beginning of the treatment the patient will have to give a new estimate of the pain on the VAS, provided that the patient didn't take a rescue medication before.

After the 2 hours, if needed usual rescue treatment can be administrated to the patient. If so, this is recorded by the investigator.

Patients will also be instructed to record the pain level 24 hours after the beginning of the treatment. They will be contacted to report this pain level and whether or not rescue medication was taken within the 24 hours following the beginning of the treatment. In case of rescue medication intake within the 24 hours following the treatment the pain level at 24 hours will not be taken into account.

4.2.4. Drop-outs, intention-to-treat and last value carried forward

a) During the treatment one-hour phase

If the patient takes rescue medication before 1 hour, it is a drop-out because the action of the medication affects the pain estimate at 1 hour.

If the patient stops the one-hour treatment and leaves the clinic, it is a drop-out because there is no pain estimate at 1 hour.

If the device stopped working accidentally, it is a drop-out because of technical reason.

On the other hand, if a patient does not get the full Cefaly acute treatment (does not want to complete the 1 hour stimulation), but stays available for the 2 hours of the protocol, this patient is kept in the trial and considered as an intention-to-treat patient (as opposed to per protocol patient).

b) During the post treatment phase

If the patient takes rescue medication before 2 hours, only the one-hour pain intensity estimate has been measured; the last value carried-forward method will be applied for 2 and 24 hours pain intensity estimate.

If the patient takes rescue medication at 2 hours or after 2 hours, the last value carried-forward will be applied for the 24 hours pain intensity estimate.

[figure not shown]

Figure 1 - Study flowchart

5. Subjects

The study will include 90 men or women.

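### A patient who stops stimulation and leaves the clinic loses the 1-hour primary score only because nobody asks for it, although the protocol already collects the same rating by contacting patients at 24 hours

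*Combined protocol and SAP*

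**What the plan says.** The primary outcome (section 3) is "Mean change of pain score at 1 hour compared to baseline". Five provisions decide whether a patient who stops early contributes to it.

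- **Section 4.2.2** lets the patient stop the stimulation and then adds: "In any case, the patient gives the estimate of the pain after 60 minutes".
- **Section 4.2.4(a)**, on leavers: "If the patient stops the one-hour treatment and leaves the clinic, it is a drop-out because there is no pain estimate at 1 hour". The missing score is the only reason given for the drop-out.
- **Section 4.2.4(a)**, on a patient who stops stimulation "but stays available for the 2 hours of the protocol, this patient is kept in the trial and considered as an intention-to-treat patient". This patient is scored and analysed.
- **Section 8.2.2** limits the ITT set to patients who used the device for more than 4 minutes and who "did not take rescue medication before the 1 hour and reported pain at 1 hour". A leaver without a score is therefore outside the primary analysis.
- **Section 4.2.3**, on the 24-hour score: "Patients will also be instructed to record the pain level 24 hours after the beginning of the treatment". It continues: "They will be contacted to report this pain level and whether or not rescue medication was taken within the 24 hours". Section 7.1 repeats the 24-hour contact, for rescue use.

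No section asks staff to obtain a leaver's 1-hour score by self-recording or by contact.

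**The concern.** The score is a single 0-10 number given by the patient. At 24 hours the protocol accepts that number when the patient records it alone and reports it on contact. At 1 hour, the time of the primary outcome, a patient who has left is not asked for it. Two patients with the same stimulation exposure are thus handled differently because one stayed in the building and the other did not.

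Leaving happens after randomisation and may depend on how the patient feels. If it does, dropping these patients makes the comparison depend on who stayed. A later change to the analysis set can readmit the patients, but it cannot supply a score that was never requested. Any value imputed for them rests on an assumption that the trial's data cannot check.

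**Working it through.** **Inputs (section 8.2.1).** The 1-hour reductions are 59% (Cefaly pilot) and 10% (placebo group of a published trial). The difference is 2.83 points, the SD 2.42, and 45 patients per group are planned. The leaver rate, the reasons for leaving and the arm are not given, so they are assumed below.

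**Reproducing the plan's figures.** For a two-sample t-test at two-sided 5% and 80% power, the 2-hour inputs (2.40, SD 2.42) give 16.98, hence 17 per group as stated. The 1-hour inputs (2.83, SD 2.42) give 12.5, hence 13. The rescue proportions (71% v 41.33%) give 43 per group without continuity correction, as stated.

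**Power.** By the normal approximation with 2.83 and SD 2.42, power is 0.9998 at 45 per group and 0.9987 at 36 per group. Losing a few patients does not threaten it.

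**Implied changes.** The baseline is not stated. It follows from 0.59b - 0.10b = 2.83:

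- b = 2.83 / 0.49 = 5.78
- verum change = 0.59 x 5.78 = 3.41
- sham change = 0.10 x 5.78 = 0.58

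**Effect of excluding leavers.** Suppose patients with a score show these changes, so that the analysed difference is 2.83. Let a fraction f of an arm leave. The all-patient difference at f = 10% is then:

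- verum leavers, no change: 0.90 x 3.41 - 0.58 = 2.49
- sham leavers, no change: 3.41 - 0.90 x 0.58 = 2.89
- verum leavers, pain resolved (change 5.78): 0.90 x 3.41 + 0.10 x 5.78 - 0.58 = 3.07
- sham leavers, pain resolved: 3.41 - (0.90 x 0.58 + 0.10 x 5.78) = 2.31
- same fraction in both arms, no change: 0.90 x 2.83 = 2.55

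The error of the analysed 2.83 is proportional to f (plus = overstated, minus = understated):

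| Who leaves, with what outcome | Error | f = 2% | f = 5% | f = 10% |
|---|---|---|---|---|
| Verum, no change | +3.41f | +0.07 | +0.17 | +0.34 |
| Sham, no change | -0.58f | -0.01 | -0.03 | -0.06 |
| Verum, pain resolved | -(5.78 - 3.41)f | -0.05 | -0.12 | -0.24 |
| Sham, pain resolved | +(5.78 - 0.58)f | +0.10 | +0.26 | +0.52 |
| Both arms equally, no change | +2.83f | +0.06 | +0.14 | +0.28 |

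In whole patients, verum leavers with no change give +0.08 for 1 of 45 (3.41/45) and +0.68 for 9 of 45. The sign depends on the arm and on the reason for leaving. The documents give neither.

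**The case against.** **The figures measure exclusion, not collection.** Section 8.2.2 names last value carried forward as its imputation method. For a leaver, the last value is the baseline, which means zero change. In the no-change rows, keeping leavers in the set with that method would remove the whole error without any contact. This is correct: the table shows the cost of exclusion. But the method works only if zero change is true. If 10% of verum patients leave with pain resolved, carrying the baseline forward gives 2.49 against 3.07, an understatement of 0.58. That is worse than the 0.24 from excluding them. Collecting the score is what removes the assumption.

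**The group may be very small.** Patients who cannot tolerate the first minutes are not included, anyone uncomfortable can hold the intensity without stopping, and those who stop but stay are retained. All of this stands. It limits how many patients are affected.

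**The two sections need not contradict each other.** Section 4.2.2 can be read as the requirement and section 4.2.4 as the label when it is not met. That reading is fair. Even so, no procedure connects the two.

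**The remote procedure exists only at 24 hours.** True. A contact timed to 60 minutes would be new, although the scale and the mode of reporting are already accepted.

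**Stronger readings that the documents do not support.** A reader might infer that leavers are the patients who did badly, so that the effect is inflated. The documents give no reasons for leaving, and a patient may leave because the pain has gone. A reader might also infer that more patients leave on verum because its stimulation is stronger. Sections 6.5 and 7.3 distinguish the sham by its low frequency, section 6.5 describes its paresthesia as similar, and no sham intensity is given.

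**Conclusion.** The point holds as an avoidable loss of the primary outcome after randomisation, possibly related to that outcome. It does not hold as a demonstrated bias in favour of the device.

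With 10% leavers in one arm, the cases worked run from an understatement of 0.24 points to an overstatement of 0.52, on a planned difference of 2.83. Verum leavers with no change give an overstatement of 0.34. These figures assume that the plan's 59% and 10% reductions describe the patients with a score, that the implied baseline of 5.78 applies to all, and that leavers either do not change or resolve completely. The leaver fraction is itself an assumption. Power remains above 0.99 throughout, so what is at stake is the validity of the comparison and its description as ITT. This is a worthwhile and inexpensive improvement, not a flaw that by itself undermines the trial.

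**What to change.** **Section 4.2.4(a).** Replace the leaver rule with the following: a patient who stops stimulation and leaves is given a score card and is contacted at 60 minutes and at 2 hours after the start of treatment. The score, and any rescue medication with its time, are entered as observed, and the CRF flags the mode of collection. The 1-hour score is missing only if the contact fails. Provide for patients who decline further contact.

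**Sections 4.2.2 and 7.1.** State that the 60-minute and 2-hour scores may be reported remotely by patients who have left.

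**Section 8.2.2.** State that the condition of having a 1-hour score is met by a remotely reported one. Without this, the collected score might still not enter the analysis.

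**Rescue.** Note that a leaver who takes rescue before 1 hour stays under the separate rescue drop-out rule in sections 4.2.4(a) and 8.2.2. The score alone does not return that patient to the analysis, though the reason for the loss is then on record.

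**Cost.** A score card, a CRF field and a few timed contacts. The drawback is that some ratings are taken outside the clinic, which the CRF flag allows to be examined. The sample size, treatment and rescue rules do not change.
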